9.2 Responsibility for Analyses/In-house Blinding

The statistical analysis of the data obtained from this study will be the responsibility of the designee/Clinical Biostatistics department of the Sponsor.

This study (through completion of the 42 days of each postvaccination safety follow-up period) will be conducted as an open-label, single-arm study, ie, participants, investigators, and Sponsor personnel will be aware of vaccination assignments after each participant is enrolled and the vaccination is assigned.

The allocation schedule will be generated by an external vendor.

9.3 Hypotheses/Estimation

Objectives and hypotheses of the study are stated in Section 3. No formal hypotheses will be tested in this study.

9.4 Analysis Endpoints

9.4.1 Immunogenicity Endpoints

The immunogenicity endpoints for VZV are:

- The response rates (defined as the percentage of participants with VZV antibody titer ≥5 gpELISA units/mL) 6 weeks postvaccination [for children] or 6 weeks postdose 2 [for adolescents/adults] among participants who are seronegative to VZV at baseline (titer <1.25 gpELISA units/mL).
- GMTs of VZV antibody as measured by gpELISA.
- The seroconversion rates (defined as the percentage of participants with VZV antibody titer ≥1.25 gpELISA units/mL) 6 weeks postvaccination [for children] or 6 weeks postdose 2 [for adolescents/adults] among participants who are seronegative to VZV at baseline (titer <1.25 gpELISA units/mL).

18-APR-2019

PRODUCT: V210
PROTOCOL/AMENDMENT NO.: 058-05

• For participants who are seropositive at baseline (baseline VZV antibody titer ≥1.25 gpELISA units/mL), the GMFR from Day 1 and the percentage of participants with ≥4-fold rise in antibody titer from Day 1 will be summarized at Day 1 and 6 weeks postvaccination for children and 6 weeks postdose 2 for adolescents/adults.

Immunogenicity summaries will be provided at Day 1 for all participants, at 6 weeks following vaccination for children, and at 6 weeks postdose 2 for adolescents and adults separately.

9.4.2 Safety Endpoints

The safety endpoints are:

- Solicited injection-site reactions (redness, swelling, pain/tenderness) of any intensity or size from Days 1 through 5 following each vaccination.
- Unsolicited injection-site AEs, regardless of severity or causality, from Day 1 through Day 42 of each postvaccination.
- Maximum reported temperature ≥39.0°C oral equivalent from Day 1 through Day 28 following each vaccination. Recorded temperatures will be converted to oral equivalents by adding 0.6°C to axillary temperatures and subtracting 0.6°C from rectal temperatures.
- Varicella-, and herpes zoster-like rashes occurring from Day 1 through Day 42 following each vaccination.
- Systemic AEs from Day 1 through Day 42 following each vaccination.
- SAEs from Day 1 through Day 42 following each vaccination.
- Vaccine-related SAEs and death from Day 1 through the end of the study for each participant (Day 42 following the last vaccination).
- A summary of blood and urine tests performed 3 days following each vaccination for participants 7 years of age and older

Unless otherwise stated, all AEs will be collected for 42 days postvaccination after each dose of VARIVAXTM.

9.5 Analysis Populations

9.5.1 Immunogenicity Analysis Populations

The Per-Protocol (PP) population will serve as the primary population for the analysis of immunogenicity data in this study. The PP population consists of all allocated participants without deviations from the protocol that may substantially affect the results of the

immunogenicity endpoint(s). Potential deviations that may result in the exclusion of a participant from the PP population for all immunogenicity analyses include:

- Missing either a baseline or postvaccination blood sample.
- Deviations from of inclusion/exclusion criteria, including:
 - Recent exposure (<4 weeks) to varicella or herpes zoster prior to vaccination (duration of exposure as defined in Section 5.2) or prior to the completion of clinical and serological follow-up in this study (exclusion from the PP population would only affect data collected subsequent to the deviation).
 - History of varicella or herpes zoster prior to study entry, or development of varicella prior to the completion of clinical and serological follow-up in this study (exclusion from the PP population would only affect data collected subsequent to the deviation).
 - Receipt of varicella or herpes zoster vaccine either alone or in combination at any time prior to the study or during the study.
 - Receipt of immune globulin, a blood transfusion, or blood-derived products (does not include autologous blood/blood products) within 5 months (150 days) prior to receipt of a study vaccine, or receipt of these products prior to completion of clinical and serological follow-up in this study (exclusion from the PP population would only affect data collected subsequent to the deviation).
 - O Age of participant at study entry is <12 months. (Deviations of the lower age limit will result in exclusion from the PP population due to the potential presence of maternal antibody, which might interfere with the evaluation of the vaccine response).
 - Any congenital or acquired immune deficiency, neoplastic disease, or depressed immunity, including those resulting from steroid use or other immunosuppressive therapy (see Section 8.1.5.2 for definition of steroid use warranting exclusion).
- Postvaccination blood sample is outside the allowable day range, which is 27 to 84 days after the associated dose of vaccine was administered for 6-week serology samples. This window for inclusion of samples in the statistical analysis is wider than the window provided earlier in this protocol (+14 days for the 6-week serology testing); however, it is being used to be consistent with other studies evaluating VZV containing vaccines.
- Participant is participating in another clinical study (other than a surveillance study).

PRODUCT: V210
PROTOCOL/AMENDMENT NO.: 058-05

• In addition, the primary analysis requires specific baseline criteria be met for VZV: antibody titer (<1.25 gpELISA units/mL).

The final determination on major protocol deviations, and thereby the composition of the PP population, will be made prior to the finalization of the database and will be documented in a separate memo.

A supportive analysis using the Full Analysis Set (FAS) population will also be performed for the immunogenicity endpoints. The FAS population consists of all allocated participants who received all study vaccinations required at the time point for the analysis and have serology result.

9.5.2 Safety Analysis Population

Safety analyses will be conducted in the All-Participants-as-Treated (APaT) population, which consists of all allocated participants who received at least one dose of study vaccine and who have some safety follow-up data after respective vaccination.

For participants 7 years of age or older, at least one laboratory measurement obtained subsequent to at least one dose of study vaccination is required for inclusion in the analysis of the respective safety parameter. For all participants, at least one temperature measurement obtained subsequent to at least one dose of study vaccination is required for inclusion in the analysis of the maximum temperature. To assess change from baseline, a baseline measurement is also required.

9.6 Statistical Methods

Statistical methods for immunogenicity and safety analyses are described in Section 9.6.1 and Section 9.6.2, respectively. No formal hypothesis will be tested in this study.

Section 9.6.3 describes how demographic and baseline characteristics will be summarized.

9.6.1 Statistical Methods for Immunogenicity Analyses

Immunogenicity summaries will be provided at baseline (prevaccination) for all participants, and at 6 weeks postvaccination for children, at 6 weeks postdose 2 for adolescents, and at 6 weeks postdose 2 for adults. The primary time points for immunogenicity summaries will be 6 weeks postvaccination for children and 6 weeks postdose 2 for adolescents/adults. For each interval, immunogenicity will be evaluated by determining baseline and postvaccination serum concentrations of VZV antibody measured by gpELISA.

The first endpoint that will be used to evaluate the immunogenicity of VARIVAX™ is response rate, which is defined as the percentage of participants with VZV-specific antibody titer ≥5 gpELISA units/mL 6 weeks postvaccination for children and 6 weeks postdose 2 for adolescents/adults, in participants who have a VZV-specific antibody titer of <1.25 gpELISA units/mL at baseline. A 95% CI for this endpoint will be calculated using the exact CI method for a single binomial proportion given in Collett [Collett, D. 1999].

PROTOCOL/AMENDMENT NO.: 058-05

The second endpoint that will be used to evaluate the immunogenicity of VARIVAXTM is the GMT. The GMT will be calculated at each time point by taking the log of the titers, averaging over all participants values, and then back-transforming to the original scale. A 95% CI for the GMTs will be calculated based on the t-distribution.

The third endpoint that will be used to evaluate the immunogenicity of VARIVAX™ is the seroconversion rate. The observed VZV seroconversion rate (the percentage of participants with VZV titer ≥1.25 gpELISA units/mL 6 weeks postvaccination for children and 6 weeks postdose 2 for adults, in participants who have a VZV–specific antibody titer of <1.25 gpELISA units/mL at baseline) will be summarized along with two-sided 95% CIs. The CIs will be computed using the exact method for a single binomial proportion given in Collett [Collett, D. 1999]. This will be computed on the PP population of participants (restricted to those with baseline titer <1.25 gpELISA units/mL) and on the FAS population (regardless of baseline status).

For participants in the PP population only, graphical displays of the reverse cumulative distribution function of antibody titers will be illustrated at 6 weeks postvaccination for children and 6 weeks postdose 2 for adolescents/adults.

Table 6 summarizes the key immunogenicity analyses. For participants who are seropositive at baseline (baseline VZV antibody titer ≥1.25 gpELISA units/mL), the following parameters and 95% CIs will be summarized at Day 1 and 6 weeks postvaccination for children and 6 weeks postdose 2 for adolescents/adults: the GMTs, the GMFR from Day 1, and the percentage of participants with ≥4-fold rise in antibody titer from Day 1. CIs will only be calculated if there are at least 5 participants who are seropositive at baseline in a given age stratum.

Endpoint/Variable (Description, Time Point)	Primary vs. Supportive Approach	Statistical Method	Analysis Population	Missing Data Approach
Summaries of response rates at 6 weeks postvaccination for children and at 6 weeks postdose 2 for adolescents and adults, separately	P	Exact One- Sample Binomial; corresponding 95% CIs	PP	Observed data only
	S		FAS	
Summaries of GMTs at 6 weeks postvaccination for children and at 6 weeks postdose 2 for adolescents and adults, separately	P	One-sample mean and 95% CI based on log-	CI based PP	Observed
	S	transformed titers and t-distribution	FAS	data only
Summaries of seroconversion rates at 6 weeks postvaccination for children and at 6 weeks postdose 2 for adolescents and adults, separately	P	Exact One- Sample Binomial: methodology,	PP	Observed data only
	S	95% CIs FAS	FAS	

Table 6 Primary Analysis Strategy for Immunogenicity Variables

CI = confidence interval; GMT = geometric mean titer; FAS = Full Analysis Set; P=Primary approach; PP = Per Protocol; S=Secondary approach.

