1 PROTOCOL SUMMARY

1.1 Synopsis

Protocol Title: An Open-Label, Multicenter, Single-arm Study to Evaluate the Immunogenicity of VARIVAXTM in Healthy Russian Individuals 12 Months of Age and Older

Short Title: Evaluation of the Immunogenicity of VARIVAXTM in Healthy Russian

Individuals

Acronym: V210-058

Hypotheses, Objectives, and Endpoints:

The following objectives and endpoints will be evaluated in Russian individuals 12 months to 75 years of age with a negative clinical history of varicella and/or herpes zoster. No formal hypotheses will be tested in the study.

V210-058-05 FINAL PROTOCOL

PRODUCT: V210

PROTOCOL/AMENDMENT NO.: 058-05

Primary Objectives

Objective: To describe the immunogenicity of VARIVAXTM after:

- Two doses of VARIVAXTM, given 6 weeks apart, in adults 18 to 75 years of age (Stage 1).
- Two doses of VARIVAXTM, given 6 weeks apart, in adolescents 13 to 17 years of age (Stage 2).
- One dose of VARIVAXTM in children 12 months to 12 years of age (Stage 2).

Primary Endpoints

Participants who are seronegative at baseline (baseline VZV antibody titer <1.25 gpELISA units/mL):

- Antibody response rate (percentage of participants with VZV antibody titer ≥5 gpELISA units/mL at 6 weeks postvaccination for children and at 6 weeks postdose 2 for adolescents/adults).
- Geometric mean titers (GMTs) of VZV antibody as measured by gpELISA at 6 weeks postvaccination for children and at 6 weeks postdose 2 for adolescents/adults.
- VZV seroconversion rate (percentage of participants with VZV antibody titer ≥1.25 gpELISA units/mL at 6 weeks postvaccination for children and at 6 weeks postdose 2 for adolescents/adults).

Participants who are seropositive at baseline (baseline VZV antibody titer ≥1.25 gpELISA units/mL):

- GMTs at Day 1 and 6 weeks postvaccination for children and at Day 1 and 6 weeks postdose 2 for adolescents/adults.
- Geometric mean fold rise (GMFR) from Day 1 to 6 weeks postvaccination for children and from Day 1 to 6 weeks postdose 2 for adolescents/adults.
- Percentage of participants with ≥4-fold rise in antibody titer from Day 1 to 6 weeks postvaccination for children and from Day 1 to 6 weeks postdose 2 for adolescents/adults.

Confidential

PRODUCT: V210

PROTOCOL/AMENDMENT NO.: 058-05

Secondary Objectives	Secondary Endpoints
Objective: To summarize the safety and tolerability of VARIVAX TM .	Following each vaccination with VARIVAX TM :

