5.1 Inclusion Criteria

In order to be eligible for the study, the participant must:

- 1. Be 12 months to 75 years of age (inclusive), at the time of signing the informed consent/assent form.
- 2. Be in good health based on medical history (physical examination is not required).
- 3. Have a negative clinical history for varicella and herpes zoster.

Female participants of reproductive potential must:

- 4. Have a negative serum pregnancy test or urine pregnancy test (sensitive to 25 mIU/mL beta human chorionic gonadotropin [β-hCG]) prior to each study vaccination (on the day the participant is vaccinated and before vaccine is administered).
- 5. Agree to remain abstinent, or use (or have their partner use) 2 acceptable methods of birth control. Abstinence or 2 acceptable methods of birth control must be practiced or used from the day of enrollment, throughout the duration of the study, and continued until 3 months following the last study vaccination. In areas where abstinence is not a locally acceptable method of contraception, 2 acceptable methods of birth control must be used through 3 months following the last study vaccination. An acceptable method of birth control is defined as: intrauterine device (IUD), oral contraception, diaphragm with spermicide, contraceptive sponge, condom, vasectomy.

Note: Female participants who are not of reproductive potential are eligible for the study without the use of contraceptives or pregnancy test. Female participants who are not of reproductive potential are defined as those who either (1) have not reached menarche; (2) have undergone hysterectomy, bilateral oophorectomy, or bilateral tubal ligation; or (3)

have reached menopause. Menopausal is defined as 1) no menses for >1 year but <3 years and confirmed by follicle stimulating hormone (FSH) levels elevated into the postmenopausal range, or 2) no menses for at least 3 years.

The participant OR the participant's legally acceptable representative must:

- 6. Understand the study procedures, alternative treatments available, and risks involved with the study, and voluntarily agrees to participate by giving written informed consent.
- 7. Provide consent for future biomedical research. However, enrollees may participate in the main study without participating in future biomedical research.
- 8. Be able to read, understand, and complete study questionnaires (eg, Vaccination Report Card [VRC]).

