8.2 Immunogenicity Assessments

Serum samples will be tested for antibody to VZV using the gpELISA assay as described in Section 8.2.2. VZV seroconversion rates, antibody response rates, and GMTs will be used as

the primary immunogenicity endpoints in this study. The seroconversion rate for VZV is defined as the percentage of participants with VZV antibody titer ≥1.25 gpELISA units/mL in participants with a baseline VZV antibody titer <1.25 gpELISA units/mL. The antibody response rate for VZV is defined as the percentage of participants with a postvaccination VZV antibody titer ≥5 gpELISA units/mL for participants whose baseline VZV antibody titer was <1.25 gpELISA units/mL. Antibody titers ≥5 gpELISA units/mL have been shown to be highly correlated with long-term protection [Kuter, B., et al 2004].

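### The supportive FAS seroconversion rate in Section 9.6.1 includes participants already seropositive at baseline, who cannot seroconvert under the plan's own definition

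*Combined protocol and SAP*

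**What the plan says.** The third endpoint paragraph of Section 9.6.1 limits seroconversion to participants with a VZV-specific "antibody titer of <1.25 gpELISA units/mL at baseline) will be summarized along with two-sided 95% CIs". Its last sentence then names two populations for the same rate: the PP population, restricted to baseline titers below 1.25, "and on the FAS population (regardless of baseline status".

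The definition is repeated elsewhere, always for seronegatives only:

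- Section 1.1 (and the matching table in Section 3) lists the seroconversion rate under "Participants who are seronegative at baseline (baseline VZV antibody titer <1.25 gpELISA units/mL".
- Section 8.2 defines it as the percentage with "VZV antibody titer ≥1.25 gpELISA units/mL in participants with a baseline VZV antibody titer <1.25 gpELISA units/mL".
- Section 9.4.1 gives it "among participants who are seronegative to VZV at baseline (titer <1.25 gpELISA units/mL".

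Table 6 carries a single row, "Summaries of seroconversion rates at 6 weeks postvaccination for children and at 6 weeks postdose 2 for adolescents and adults, separately", with PP as the primary approach and FAS as the supportive one. It has no note on denominators.

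Seropositive participants are expected. Entry depends on clinical history (Section 5.1: "Have a negative clinical history for varicella and herpes zoster"), not on serology. The FAS definition in Section 9.5.1 has no serostatus condition. Section 9.6.1 gives seropositives their own summaries: "the GMTs, the GMFR from Day 1, and the percentage of participants with ≥4-fold rise in antibody titer from Day 1".

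**The concern.** The definition and the FAS instruction stand in one paragraph and cannot both hold. The threshold is 1.25 gpELISA units/mL both for being seronegative at baseline and for having converted. A participant at or above 1.25 on Day 1 therefore cannot convert, yet enters the FAS denominator and, if the titer holds, the numerator. What the instruction produces is the percentage of all FAS participants with a titer of at least 1.25 at six weeks. That is a legitimate summary, but it is not a seroconversion rate.

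The FAS analysis is there to support the PP result. As written, a difference between the two rates mixes the effect of the PP exclusions with the effect of adding participants who were already positive. If seropositives stay positive, the shift can only raise the rate, and the larger denominator lifts the lower confidence limit further. The exact interval is valid for the all-comers percentage but not for seroconversion. Section 4.2 intends comparison with existing global data, so a figure labelled seroconversion should have the defined denominator.

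**Working it through.** **Inputs.** The definition, populations and interval method come from Sections 9.5.1 and 9.6.1; the hypothetical GMTs and SD of 1.0 for log titers from Table 8; the hypothetical response rates from Table 7. The documents do not give the seropositive share *s* or the seroconversion rate *p*, so both are assumptions below.

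**Step 1: excess of the reported rate.** Let *q* be the share of seropositives at or above 1.25 at six weeks. The FAS figure is (1 − s)p + sq. With q = 1 (assumed) this is p + s(1 − p), so the excess over p is s(1 − p). It is zero if s = 0 or p = 1.

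**Step 2: scale of the SD in Table 8.** For GMT 80 and n = 40, exp(ln 80 ± t(0.975, 39)/√40) = 58.1 to 110.1, as Table 8 states. The SD of 1.0 is therefore on the natural-log scale; on the log10 scale the limits would be 38.3 to 167.1.

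**Step 3: *p* implied by Table 8.** Assuming log-normal titers, P(≥1.25) = Φ(ln(GMT/1.25)).

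| Group | GMT | p | Excess, s = 20% | Excess, s = 50% |
|---|---|---|---|---|
| Children | 10 | 0.9812 | 0.38 point | 0.94 point |
| Children | 12 | 0.9881 | 0.24 point | 0.60 point |
| Children | 14 | 0.9922 | 0.16 point | 0.39 point |
| Adults, adolescents | 80 | 0.99998 | below 0.001 point | below 0.001 point |

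For GMT 100 and 120, p is higher still. With 60 children one participant is 1/60 = 1.7 points, so even the largest of these shifts is worth less than one participant.

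**Step 4: how firm *p* is.** By the same formula with a cut-off of 5, Table 8 implies P(≥5) = 0.997 at GMT 80, whereas Table 7 uses 0.80 to 0.92 for adults and adolescents. The two tables do not describe one titer distribution, so p is uncertain in those groups. The unfavourable extreme is p = 0.80, which needs a response rate at 5 of 0.80 and nobody between 1.25 and 5. The excess at s = 20% is then 0.20 × 0.20 = 4 points.

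**Step 5: effect on counts and exact 95% intervals.** Take 40 seronegatives plus 10 seropositives (s = 20%), with all seropositives staying at or above 1.25. The interval for 32/40 agrees with Table 7 (adults, n = 40, rate 0.80: 0.64 to 0.91).

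| Seronegatives only | As Section 9.6.1 would report |
|---|---|
| 32/40 = 80% (64.4 to 90.9) | 42/50 = 84% (70.9 to 92.8) |
| 39/40 = 97.5% (86.8 to 99.9) | 49/50 = 98% (89.4 to 99.9) |
| 40/40 = 100% (91.2 to 100) | 50/50 = 100% (92.9 to 100) |

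Near 100% the rate hardly moves; the lower limit rises by 1.7 to 2.6 points.

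**The case against.** The best defence is that the wider denominator is deliberate and disclosed. Section 9.6.1 states the two denominators side by side, and Section 9.5.1 ties the baseline titer criterion to the primary analysis, so an FAS that lifts it along with the other PP conditions is coherent. On that view only a label is wrong, and renaming the row would be enough. The effect is also close to nil on the Table 8 figures, and the 4-point case borrows a hypothetical response rate at the cut-off of 5. Finally, baseline serostatus is reported (Section 9.6.3) and seropositives are summarized separately, so a reader could largely disentangle a PP–FAS difference.

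Much of this stands. An all-comers summary is legitimate, the likely size is small, and the 4-point case is an extreme rather than an expectation. But a wider population does not change what the endpoint measures, and neither the disclosure in one parenthesis nor the separate summaries remove the contradiction with the definition. Renaming alone would be accurate, but the plan would then have no explicit FAS seroconversion rate to set against the PP rate.

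A further objection is that Table 6 also lists an FAS row for GMTs without stating a baseline condition. That is fair, but it is a separate matter that this correction does not settle.

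**Conclusion.** The concern holds and is minor. As written, the FAS figure counts already-seropositive participants as seroconverters, and no other section reconciles it with the definition.

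On the titers implied by Table 8, with 20% to 50% seropositive at baseline, the excess is 0.16 to 0.94 point in children and negligible in adults and adolescents; the unfavourable extreme at 20% seropositive is 4 points. These sizes rest on assumed seropositive shares, log-normal titers and all seropositives staying at or above 1.25.

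The primary PP seroconversion rate is correctly restricted. The response rate and the precision tables are not touched by this sentence, and no decision rule depends on it because no hypothesis is tested.

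**What to change.** In Section 9.6.1, replace the parenthesis after the FAS with a restriction to FAS participants whose baseline titer is below 1.25 gpELISA units/mL. If an all-comers figure is also wanted, report it in addition, in its own row of Table 6, as the percentage with a titer of at least 1.25 gpELISA units/mL, not as seroconversion.

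No new data are needed: Section 8.2.1 makes the Day 1 sample mandatory for enrollment. The FAS denominator becomes smaller and its interval wider (in the example above, a lower limit of 91.2% at 40/40 instead of 92.9% at 50/50). An FAS participant without a usable Day 1 result drops out of this rate. The edit should be recorded by whichever route in the opening of Section 9 applies, a protocol amendment or a supplemental SAP.
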